### **7.6.9 Other Events of Special Interest**

OEOSI will be summarized by treatment group for each category.

The following analyses will be conducted using the 100-day safety window:

- Overall summary of OEOSI by worst CTC grade (any grade, grade 3-4, grade 5) presented by Category / PT

- Overall summary of drug-related OEOSI by worst CTC grade (any grade, grade 3-4, grade 5) presented by Category / PT

A by-subject listing of OEOSI will be provided.

### **7.6.10 Adverse Events of pneumonitis and lung disease**

The following adverse events will be summarized by treatment group:

- Interstitial Lung Disease
- Pneumonitis
- Immune-Mediated Pneumonitis

The following analyses will be conducted using the 100-day safety window:

- Overall summary by worst CTC grade (any grade, grade 3-4, grade 5) presented by Category / PT

A by-subject listing will be provided.

### **7.6.11 Multiple Events**

The following summary tables will be provided:

- A table showing the total number and rate (exposure adjusted) of occurrences for all AEs.
- A table showing the total number and rate (exposure adjusted) of occurrences for AEs occurring in at least 5% of subjects in any treatment group.

A listing displaying the unique instances of all AEs, i.e., after duplicates have been eliminated and overlapping and contiguous occurrences of the same event (i.e. same PT) have been collapsed will be provided. No formal comparisons will be made between treatment groups.

### **7.6.12 Laboratory Parameters**

In the laboratory summary tables, unless otherwise specified, subjects will be counted only once for each lab parameter according to their worst on treatment CTC grade (worst being the highest CTC grade). The laboratory tables and listings will be sorted by laboratory category, laboratory subcategory and laboratory test code sequence number.

The analysis population for each laboratory test is restricted to treated subjects who underwent that laboratory test. Laboratory tests (in addition to the tests specified below) with CTC criteria collected in the specific studies may also be included in the summaries.

A by-subject listing of differences in categorization of SI and US laboratory test results will be provided.

The analyses will be conducted using the 30-day.

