Targeted PE, Measurements, Vital Signs, and ECOG PS	X	X	Weight, BP, HR, temperature, and ECOG PS. Targeted PE may include ocular examination, if clinically indicated.
AE Assessment (including SAEs)	X	X	Participants will be followed for treatment-related toxicities until these toxicities resolve, return to baseline, or are deemed irreversible. Note: All AEs will be documented for a minimum of 100 days after last dose of nivolumab for Safety Run-in Cohorts and Arms A and B, and for 30 days from the last dose of study treatment for Arm C.
Concomitant Medication Review	X	X	Record at each visit.
Subsequent Cancer Treatment	X	X	At each visit, record any new surgery, radiotherapy, and systemic cancer therapy given for the disease under study.
Laboratory Tests			
CBC with Differential, Chemistry, and Endocrine	X	X	Must be performed at FU1. If study drug-related toxicities persist, must be repeated at FU2. See Section 9.4.4 (Clinical Safety Laboratory Assessments) for list of laboratory tests to conduct.

Abbreviations: AE = adverse event; BP = blood pressure; CBC = complete blood count; ECOG = Eastern Cooperative Oncology Group; eCRF = electronic case report form; FU1 = follow-up visit 1; FU2 = follow-up visit 2; HR = heart rate; ██████████ IV = intravenous; PE = physical examination; ██████████ PS = performance status; SAE = serious adverse event; SOC = standard of care.

^a Participants must be followed for at least 100 days after last dose of nivolumab. FU1 should occur 30 days (± 7 days) from the last dose of any treatment (IV or oral whichever comes later). FU2 occurs approximately 100 days (± 7 days) from last dose of nivolumab. Both follow-up visits should be conducted in person.

^b Some of the assessments referred to in this section may not be captured as data in the eCRF. They are intended to be used as safety monitoring by the treating physician. Additional testing or assessments may be performed as clinically necessary or where required by institutional or local regulations.

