- On-treatment evaluations (laboratory tests, pulse oximetry and vital signs) will be defined as evaluations taken after the day (and time, if collected and not missing) of first dose of study treatment. For subjects who are off study treatment, evaluations should be within a safety window of 30 days (or 100 days depending on the analysis) after the last dose of study treatment.

•

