### **7.10 Analyses at the time of the decision for the dose level to be evaluated in the randomized phase.**

At the time of the analysis for the selection of the dose to be evaluated in the randomized phase of the study (see paragraph Schedule of Analyses in [Section 1](#) for the timing of the analysis), the following analyses will be produced using all available data from the safety run-in phase:

- Summary and listing of the relevant protocol deviations during the safety run-in phase
- Summaries and listings of subject disposition for each study period of the safety run-in phase
- Summaries of demographic and baseline disease characteristics
- Listing of medical history
- Summaries and listings of prior therapy agents
- Listing of physical examinations
- Summaries and listings of administration of study therapy
- Summaries of modifications of study therapy
- Summary and listing of concomitant medications
- Summary and listing of dose-limiting toxicities
- Summary and listing of deaths
- Summaries of SAEs, drug-related SAEs, AEs leading to discontinuation, drug-related AEs leading to discontinuation, AEs leading to dose delay/reduction, drug-related AEs leading to dose delay/reduction, AEs, drug-related AEs, any select AEs, any non-endocrine and endocrine IMAEs where immune modulating medication was initiated, OEOSI, AEs of Interstitial Lung

Disease (ILD), pneumonitis and immune-mediated pneumonitis. All these summaries will be presented by worst CTC grade (any grade, grade 3-4, grade 5) using the 30 days safety window.

- Listing of AEs
- Summary and listing of marked laboratory abnormalities in both US and SI units using the 30 days safety window.

At the time of this analysis, the safety run-in phase will not be completed. A clinical study report may not be prepared at this point. For the analyses for the clinical study report, the full set of analyses for the safety run-in phase, as described in this statistical analysis plan, will be produced when all patients in the safety run in phase either completed the study duration or discontinued from it.

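### The protocol allows the mandatory FU1 blood sample on days 23 to 37 after the last dose, but the SAP's laboratory tables stop at day 30, so compliant samples from days 31 to 37 are not counted.

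*SAP*

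**What the plan says.** **Visit and sample.** Protocol Section 2, Table 2-3, footnote a: "FU1 should occur 30 days (± 7 days) from the last dose of any treatment (IV or oral whichever comes later". The laboratory row of that table says: "Must be performed at FU1. If study drug-related toxicities persist, must be repeated at FU2". On FU2, footnote a says: "FU2 occurs approximately 100 days (± 7 days) from last dose of nivolumab". FU2 applies to the run-in and Arms A and B only.

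**Which values count.** SAP 6.1, for participants who have stopped dosing: "evaluations should be within a safety window of 30 days (or 100 days depending on the analysis) after the last dose of study treatment". SAP 7.6.12 picks the window in a sentence that ends early: "The analyses will be conducted using the 30-day". The same section sets the counting rule: "subjects will be counted only once for each lab parameter according to their worst on treatment CTC grade". SAP 7.10, for the dose-decision analysis, names the window in full: "Summary and listing of marked laboratory abnormalities in both US and SI units using the 30 days safety window". The hepatic and thyroid summaries in SAP 7.6.12.4 are also confined to on-treatment evaluations. The text available gives no visit-window allowance for laboratory values and no 100-day repeat of the laboratory tables.

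**Other scheduled samples.** Protocol Table 2-2 places laboratory tests on Day 1 of every cycle and Day 15 of Cycles 1 and 2. Its pre-surgery column has none.

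**The concern.** Both documents count from the last dose of study treatment. Anastrozole taken after Cycle 5 or end of treatment is classed as concomitant medication, so it does not move that date. The protocol therefore asks for a sample on a day that the SAP may then treat as too late to tabulate.

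For a participant who completes treatment, the previous scheduled sample is the one for Cycle 5 Day 1, taken before that day's dosing. It cannot reflect Cycle 5 palbociclib or a nivolumab infusion given in that cycle. FU1 is the first scheduled sample that can. Whether a late change in transaminases, bilirubin, creatinine, TSH or blood counts reaches the tables would then depend on the day the visit happened to be booked. Laboratory abnormalities are part of the secondary safety endpoint in Protocol Section 4 and SAP 4.2.4.

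**Working it through.** The plan gives no figure for how many FU1 samples fall inside or outside the window, so there is nothing of its own to reproduce.

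**Inputs**
- FU1 at 30 ± 7 days after the last dose of any study treatment (Protocol Table 2-3).
- Cut-off at 30 days after the last dose of study treatment (SAP 6.1 and 7.6.12, with 7.10 supporting the reading).
- Day 30 is taken as inside the window. The exposure formula in SAP 7.1.1 adds 31 days to (last dose − first dose), which includes the 30th day after the last dose.
- The distribution of actual FU1 days is in neither document and has to be assumed.

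**Step 1: permitted days**
- Days 23 to 37: 37 − 23 + 1 = 15 days.
- Counted, days 23 to 30: 8 days.
- Not counted, days 31 to 37: 7 days, or 7/15 = 46.7% of permitted days. This is a share of days, not of samples.

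**Step 2: share of samples under assumed visit patterns**

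Give day d (23 to 37) the weight Φ((d + 0.5 − μ)/σ) − Φ((d − 0.5 − μ)/σ), rescale the weights to sum to 1, and add those for days 31 to 37. For μ = 30 and σ = 1 this is essentially P(Z > 0.5) = 0.309.

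| Centre μ | SD σ | Share on days 31–37 |
|---|---|---|
| 30 | 1 | 31% |
| 30 | 2 | 40% |
| 30 | 3 | 43% |
| 30 | 4 | 45% |
| 30 | 5 | 45% |
| 27 | 3 | 13% |
| 28 | 3 | 21% |
| 32 | 3 | 68% |
| 33 | 3 | 78% |

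The logical limits are 0% and 100%. The centre of the distribution matters far more than its spread.

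**Step 3: what else is scheduled late**

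Assume a participant receives nivolumab on Cycle 5 Day 1 and takes anastrozole through Cycle 5 Day 28, 27 days later.
- Cycle 5 Day 1 to FU1: 27 + 23 = 50 days to 27 + 37 = 64 days, with no other scheduled laboratory test between them.
- FU2, counted from the last oral dose: 93 − 27 = 66 to 107 − 27 = 80 days. These conditional repeats lie wholly outside a 30-day window.
- Arm C has no FU2, so FU1 is its only scheduled follow-up sample.

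**Step 4: effect of moving the cut-off to day 37**

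Permitted FU1 days not counted fall from 7 of 15 to 0 of 15.

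**The case against.** **A 30-day cut-off is a defensible attribution rule.** Surgery is due within 4 weeks of the last neoadjuvant dose, so for participants on schedule days 31 to 37 are post-operative, and adjuvant treatment may have begun. Counting those values as on-treatment can bring surgical or adjuvant effects into the worst-grade tables. This stands, and it is the reason to keep the 30-day tables as well.

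**Other outputs cover part of the gap.** The by-subject listings in SAP 7.6.12.1 to 7.6.12.3 are not expressly limited to 30 days. Protocol 9.2.6 requires clinically important laboratory results to be recorded as adverse events. The SAP repeats the drug-related adverse event summary at 100 days (7.6.6) and uses 100 days for immune-mediated events (7.6.8), including hepatitis, renal dysfunction and thyroid events. This also stands. The cover is thinner for Arm C, where Protocol 9.2.2 collects non-serious adverse events for only 30 days after the last dose.

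**The wording is uncertain.** The key sentence is unfinished, SAP 6.1 allows either 30 or 100 days, and SAP 4.2.4 points to a core SAP that is not available here. A visit-window convention there cannot be ruled out. Even so, 7.10 uses 30 days for laboratory data, and nothing in the SAP text points to 100.

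**Stronger readings that the documents do not support**
- *Nearly half the FU1 samples are lost, or about 51 of 110 participants* (110 × 7/15 = 51.3). This needs full attendance and visits spread evenly over the window. Neither is documented.
- *FU1 is the only sample after Cycle 5.* FU2 tests are required when drug-related toxicity persists, and extra tests are allowed. FU1 is the only one mandatory for all.
- *Participants drop out of the tables.* They stay in through their Cycle 1 to 5 samples. What is lost is one sample.
- *Each affected participant has a nivolumab dose with no later tabulated value.* Arm C receives no nivolumab. A participant whose Cycle 5 infusion was omitted already has the Cycle 5 Day 1 sample after the last infusion.

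**Conclusion.** The mismatch is real on the text available: a sample that the protocol requires and accepts as on time can fall outside the SAP's laboratory tables solely because of its draw date. Seven of the 15 permitted days are affected. The share of samples is unknown and depends on when sites book FU1.

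The consequence is limited to the descriptive laboratory summaries: worst grade, shift, hepatic and thyroid. A count changes only where FU1 would have given the participant's worst grade or a qualifying abnormality, and the documents give no basis for estimating how often. No efficacy result is touched, and the same cut-off applies to every arm.

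The conclusion assumes that the unfinished sentence means the 30-day safety window, that day 30 is inside it, and that the core SAP adds no visit-window rule. With those assumptions it should be corrected before database lock. It concerns a stated secondary safety endpoint, and the data are already being collected.

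**What to change.** 1. Complete the sentence in SAP 7.6.12 so that the window is stated.
2. In SAP 6.1, 7.6.12 and 7.6.12.4, state that the laboratory summaries include the nominal FU1 sample when it is drawn within its permitted window, that is, through day 37 after the last dose of study treatment. Apply the rule identically to Arms A, B and C and to the run-in.
3. Keep the strict 30-day version as a companion table, so that a reader can see whether any difference comes from samples taken after surgery or after adjuvant therapy began.

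A plain 100-day window would also capture FU1. It would, however, add FU2 values that exist only for participants with persisting toxicity and never in Arm C, so FU1 is the cleaner common rule.

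The cost is one sentence of SAP text, one laboratory analysis flag and a second run of the tables. No new samples or visits are needed. The small downside is that some values drawn up to 7 days later are counted as on-treatment, and the companion table makes that visible.

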#### **7.6.12.1 Hematology**

The following will be summarized by treatment group as worst CTC grade on-treatment per subject and as shift table of worst on-treatment CTC grade compared to baseline CTC grade per subject: hemoglobin (HB), hematocrit, total leukocyte count (including differential), platelets, white blood counts (WBC), absolute neutrophils count (ANC) and lymphocyte count (LYMPH).

A by-subject listing of these laboratory parameters will be provided.

### **7.6.12.2 Serum Chemistry**

The following will be summarized by treatment group as worst CTC grade on-treatment per subject: ALT, AST, alkaline phosphatase (ALP), lactate dehydrogenase (LDH), total bilirubin, creatinine, blood urea nitrogen (BUN) or serum urea, lipase and amylase.

A by-subject listing of these laboratory parameters will be provided.

### **7.6.12.3 Electrolytes**

The following will be summarized by treatment group as worst CTC grade on-treatment per subject and as shift table of worst on-treatment CTC grade compared to baseline CTC grade per subject: sodium (high and low), potassium (high and low), chloride (high and low), calcium (high and low), phosphorus (high and low), and Glucose Serum (fasting hyperglycemia and hypoglycemia regardless of fasting status).

A by-subject listing of these laboratory parameters will be provided.

### **7.6.12.4 Additional Analyses**

In addition, further analyses on specific laboratory parameters will be performed by treatment group:

#### Abnormal Hepatic Function Test

The number of subjects with the following laboratory abnormalities from on-treatment evaluations will be summarized by treatment group:

- ALT or AST > 3 x ULN, > 5 x ULN, > 10 x ULN and > 20 x ULN
- Total bilirubin > 2 x ULN
- ALP > 1.5 x ULN
- Concurrent (within 1 day) ALT or AST > 3 x ULN and total bilirubin > 1.5 x ULN
- Concurrent (within 30 days) ALT or AST > 3 x ULN and total bilirubin > 1.5 x ULN
- Concurrent (within 1 day) ALT or AST > 3 x ULN and total bilirubin > 2 x ULN
- Concurrent (within 30 days) ALT or AST > 3 x ULN and total bilirubin > 2 x ULN

A by-subject listing of these specific abnormalities will be provided.

#### Abnormal Thyroid Function Test

The number of subjects with the following laboratory abnormalities from on-treatment evaluations will be summarized by treatment group:

- TSH value > ULN and
  - with baseline TSH value ≤ ULN
  - with at least one FT3/FT4 test value < LLN within 2-week window after the abnormal TSH test
  - with all FT3/FT4 test values ≥ LLN within 2-week window after the abnormal TSH test

- with FT3/FT4 missing within 2-week window after the abnormal TSH test.
- TSH < LLN and
  - with baseline TSH value  $\geq$  LLN
  - with at least one FT3/FT4 test value > ULN within 2-week window after the abnormal TSH test
  - with all FT3/FT4 test values  $\leq$  ULN within 2-week window after the abnormal TSH test
  - with FT3/FT4 missing within 2-week window after the abnormal TSH test

A by-subject listing of these specific abnormalities will be provided.

### **7.6.13 Vital Signs and Pulse Oximetry**

Vital signs and pulse oximetry (i.e. % oxygen saturation) collected on the CRF will be provided in separate listings.

### **7.6.14 Physical Measurements**

Physical measurements will be listed by subject.

### **7.6.15 Electrocardiograms (ECG) /ECHO or MUGA**

[figure not shown]
A by-subject listing of ECG abnormalities and the corresponding grading information will be provided.

[figure not shown]
#### Normal ranges for ECG parameters

- HR: 60 to 100 beats per minute
- PR interval: 120-200 milliseconds
- QRS complex: 80-100 milliseconds
- QT interval: 390-450 milliseconds in men; 390-460 milliseconds in women
- QTcB and QTcF:  $\leq$  430 milliseconds in men;  $\leq$  450 milliseconds in women

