Definition of DLTs: DLTs are defined as any TEAEs specified below that occur during the first 4 weeks (1 cycle) except those clearly and incontrovertibly due to disease progression or extraneous causes.

Gastrointestinal DLTs

- Grade 2 colitis that lasts longer than 7 days, despite best supportive treatment.
- Grade 3 diarrhea or colitis that lasts longer than 72 hours with adequate supportive treatment.
- Grade ≥ 4 diarrhea or colitis.

Hepatic DLTs

- Grade 4 elevations in serum transaminases (aspartate aminotransferase [AST] and alanine aminotransferase [ALT], alkaline phosphatase [ALP]) or total bilirubin.
- Grade 3 elevations in serum AST, ALT, or bilirubin.
- Bilirubin $> 2 \times$ upper limit of normal (ULN) in the absence of cholestasis.
- Grade 2 elevations in AST or ALT with symptomatic liver inflammation (eg, right upper quadrant tenderness, jaundice).
- Grade 3 ALP elevation that last longer than 5 days, or is associated with clinical symptoms.
- AST or ALT $> 3 \times$ ULN and concurrent total bilirubin $> 2 \times$ ULN without initial findings of cholestasis (elevated ALP; eg, findings consistent with Hy's law or FDA definition of potential drug-induced liver injury [p-DILI]). Note that this specific category of DLT uses ULN rather than NCI CTCAE grade for definition.

Hematologic DLTs

- Grade 4 neutropenia ≥ 7 days in duration.
- Grade 4 thrombocytopenia.
- Grade 3 thrombocytopenia with bleeding or any requirement for platelet transfusion.
- Grade 3 hemolysis (ie, requiring transfusion or medical intervention such as steroids).
- Neutropenic fever of any duration.
- Grade 4 anemia not explained by underlying disease.

Dermatologic DLTs

- Grade 4 rash or confirmed Stevens-Johnson Syndrome or Toxic Epidermal Necrolysis.
- Grade 3 rash if no improvement (ie, resolution to \leq Grade 1) after a 1- to 2-week infusion omission for nivolumab.

Other DLTs

- Recurrence of same Grade 3 adverse reactions.

- Any AE that required discontinuation of nivolumab per approved label.
- Any Grade immune-related encephalitis.
- Any incidence of Grade ≥ 3 prolongation of QT interval corrected using Fridericia's Correction Formula (QTcF) on electrocardiograms (ECGs). Grade 3 hypersensitivity reaction/infusion reaction that does not resolve to Grade 1 in < 6 hours.
- Grade 2 pneumonitis that does not respond to dose modification for nivolumab and systemic steroids within 14 days.
- Any death not clearly due to the underlying disease or extraneous causes.

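### The SAP's normal ranges for QT and corrected QT contradict each other over much of its own normal heart-rate range, so an ECG-abnormality listing built on them would report rate-appropriate QT values as abnormal

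*SAP*

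**What the plan says.** SAP 7.6.15 (Electrocardiograms/ECHO or MUGA) states: "A by-subject listing of ECG abnormalities and the corresponding grading information will be provided". Beneath it, under "Normal ranges for ECG parameters", the SAP gives:

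- Heart rate: "HR: 60 to 100 beats per minute".
- Uncorrected QT: "QT interval: 390-450 milliseconds in men; 390-460 milliseconds in women". The lower limit is 390 ms for both sexes and does not vary with heart rate.
- QTcB and QTcF together: at most "430 milliseconds in men" and at most 450 ms in women, with no lower limit.

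The text available contains no sentence saying how these ranges select records for the listing, and shows no other use for them. The correction formulas are not written out.

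The protocol uses corrected QT in two places. Section 5.1.2.1 makes Grade 3 or higher "prolongation of QT interval corrected using Fridericia's Correction Formula (QTcF) on electrocardiograms (ECGs" a DLT, graded by CTCAE v5.0. Section 6.2 excludes a screening corrected QT above 470 ms without naming the correction. Table 2-2 schedules triplicate ECGs at Cycle 1 Day 1 and Cycle 1 Day 15, and otherwise as clinically indicated.

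**The concern.** Uncorrected QT shortens as heart rate rises; that is why it is corrected. A fixed QT floor beside a ceiling on corrected QT can be consistent only up to some heart rate. If that rate lies inside the SAP's own 60-100 bpm range, an ECG above it must fail one limit or the other, whatever the heart is doing.

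At stake is the usefulness of one safety listing. A programmer who applies the ranges literally would list participants for a QT below 390 ms when their heart rate and both corrected values are within the SAP's limits. A safety reader would then have to sort those entries from the ones that matter.

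**Working it through.** The plan states no figure to reproduce here. The check asks whether its stated limits can hold together.

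**Inputs (SAP 7.6.15).** Heart rate 60-100 bpm; QT floor 390 ms; QT ceiling 450 ms (men) or 460 ms (women); QTc ceiling L = 430 ms (men) or 450 ms (women), applied to both QTcB and QTcF.

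**Formulas (standard definitions, assumed).** With RR = 60/HR in seconds, QTcB = QT/RR^(1/2) (Bazett) and QTcF = QT/RR^(1/3) (Fridericia).

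**Step 1: highest heart rate at which QT ≥ 390 and QTc ≤ L can both hold.** Setting QT = 390 and QTc = L gives HR = 60 × (L/390)² for Bazett and 60 × (L/390)³ for Fridericia.

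| | Bazett | Fridericia |
|---|---|---|
| Men, L = 430 | 60 × (430/390)² = 72.9 bpm | 60 × (430/390)³ = 80.4 bpm |
| Women, L = 450 | 60 × (450/390)² = 79.9 bpm | 60 × (450/390)³ = 92.2 bpm |

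Because the SAP applies the ceiling to both corrections, Bazett binds above 60 bpm.

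**Step 2: how much of the normal heart-rate range is affected.** The share of its width above each cut-off is (100 − cut-off)/40. By Bazett this is 27.1/40 = 68% for men and 20.1/40 = 50% for women. By Fridericia it is 19.6/40 = 49% and 7.8/40 = 20%. These are shares of the range, not of ECGs.

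**Step 3: examples.**

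- QT 390 ms at 75 bpm gives QTcB 436.0 and QTcF 420.1. For a man, QTcB is abnormal.
- QT 390 ms at 100 bpm (RR 0.6 s) gives QTcB 390/0.6^(1/2) = 503.5 and QTcF 390/0.6^(1/3) = 462.4. Both exceed the limit for either sex.
- At 100 bpm, QTcB is within its limit only if QT is at most 430 × 0.6^(1/2) = 333 ms (men) or 450 × 0.6^(1/2) = 349 ms (women), well below 390 ms.
- QT 360 ms at 80 bpm (RR 0.75 s) gives QTcB 360/0.75^(1/2) = 415.7 and QTcF 360/0.75^(1/3) = 396.2. Heart rate and both corrected values are in range for either sex, yet QT is below 390 ms.

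**Step 4: low-QT flags below the cut-offs.** QT is under 390 ms whenever QTcF is below 390/RR^(1/3). That threshold is 410.6 ms at 70 bpm and 429.3 ms at 80 bpm. So in-range QTcF values already coincide with a low QT at rates where the two limits can still be met together.

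**Step 5: the upper limits.** At 60 bpm RR is 1 s and QT = QTc. A QT of 431-450 ms (men) or 451-460 ms (women) is then normal as QT and abnormal as QTc. A QT at its ceiling meets the QTc limit only at or below 60 × (430/450)² = 54.8 bpm (men) or 60 × (450/460)² = 57.4 bpm (women) by Bazett, and lower still by Fridericia. All of these lie below the normal heart-rate range.

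**The case against.** The strongest objection concerns consequence, not arithmetic. No sentence ties the ranges to the listing, and figures are missing from the available text around the listing sentence, so a selection rule or further ECG output may exist unseen. This stands. The link is an inference from placement, and the ECG listing cannot be called the only planned ECG output. The contradiction between the ranges does not depend on that link.

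A reader might also infer that false low-QT entries would hide real QTcF prolongation. The documents do not support that:

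- The DLT criterion uses graded QTcF, not these ranges, and DLTs have their own summary and listing (SAP 7.6.1, repeated for dose selection in 7.10).
- Significant ECG worsening must be recorded as an adverse event (Protocol 9.2.8), and adverse events are tabulated by grade and listed (SAP 7.6.6).
- The ECG listing carries grading information, and a low-QT flag does not remove a high-QTcF flag.

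It is fair to say the Bazett cut-offs are the more extreme pair, while the protocol's DLT criterion uses Fridericia. Both pairs belong in the point, and the conflict falls within 60-100 bpm under either.

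A frequency is tempting but cannot be taken from the documents. Assume QTcF with mean 400-420 and SD 18 ms, and heart rate with mean 68-76 and SD 10 bpm, limited to 60-100. Simulation then puts QT below 390 ms in 40-83% of ECGs with QTcF at or below 450 ms. That rests wholly on assumed distributions. It also measures how often the QT floor is missed, not how often the limits are mutually unattainable, so the conclusion does not use it.

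**Conclusion.** The normal ranges in SAP 7.6.15 are internally inconsistent as written. On the SAP's own numbers and the standard correction formulas, no ECG can meet both the QT floor and the QTc ceiling above 72.9 bpm (men) or 79.9 bpm (women) by Bazett, or above 80.4 and 92.2 bpm by Fridericia. The QT ceilings conflict with the QTc ceilings from 60 bpm upward.

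The reporting consequence is conditional. If the ranges select the listed records, ECGs with normal heart rate and normal QTc will appear as abnormal for low QT. How many is unknown. The effect stops at descriptive safety reporting: DLT decisions, eligibility and the efficacy estimates do not use these ranges. It is worth correcting because the error is plain and cheap to remove, not because it threatens a trial conclusion.

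**What to change.** In SAP 7.6.15, state which parameters place a record in the listing, and remove the fixed uncorrected-QT range as a trigger. Base the repolarisation flag on corrected QT, with QTcF and its CTCAE v5.0 grade as the main flag, since QTcF is the measure the protocol already uses for its DLT criterion. QTcB may stay as a supporting value, and uncorrected QT can still be displayed. Heart rate, PR and QRS flags need no change on this account.

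Deleting QTcB altogether, averaging the triplicates, or adding change from baseline would be preferences; the inconsistency does not require them.

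The cost is a few lines of SAP text and a small programming change, with no new data and no effect on the conduct of the trial.
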